## Appendix III: Patient Cosmesis Form

INSTRUCTIONS: The first page of this form is completed by the clinical staff. You have been treated with breast conserving therapy for breast cancer. As you know, a reason for choosing this treatment is to keep a breast that looks and feels as close to normal as possible. Your opinion concerning the appearance of your breast is valuable to us. This form will be confidential. Circle the number next to the word that best describes how your breast looks now. Circle only one answer per question. Use -1 for N/A or unknown unless otherwise specified. Dates are recorded mm/dd/yyyy unless otherwise specified.
		 DE

1 _____ DATE QUESTIONNAIRE COMPLETED
 
2      1 EXCELLENT: when compared to the untreated breast or the original appearance of the breast, there is minimal or no difference in the size or shape of the treated breast. The way the breast feels (its texture) is the same or slightly different. There may be thickening, scar tissue or fluid accumulation within the breast, but not enough to change the appearance.
 
2 GOOD: there is a slight difference in the size or shape of the treated breast as compared to the opposite breast or the original appearance of the treated breast. There may be some mild reddening or darkening of the breast. The thickening or scar tissue within the breast causes only a mild change in the shape or size.
 
3 FAIR: obvious differences in the size and shape of the treated breast. This change involves a quarter or less of the breast. There can be moderate thickening or scar tissue of the skin and the breast, and there may be obvious color changes.
 
4 POOR: marked change in the appearance of the treated breast involving more than a quarter of the breast tissue. The skin changes may be obvious and detract from the appearance of the breast. Severe scarring and thickening of the breast, which clearly alters the appearance of the breast, may be found.
		
3 MY SATISFACTION ABOUT THE TREATMENT AND RESULTS IS:(CIRCLE THE NUMBER NEXT TO THE ITEM THAT BEST DESCRIBES YOUR SATISFACTION.)
 
1 I am totally satisfied with the treatment and results
 
2 I am not totally satisfied, but would choose brachytherapy (radioactive implants) again
 
3 I am not totally satisfied and would choose the standard 5 or 6 weeks of external beam therapy if I had it to do over again
 
4 I am dissatisfied with the brachytherapy (radioactive implants)
 
4 BEFORE ANY TREATMENT TO YOUR BREAST, THE SIZE OF YOUR BREASTS WAS (CIRCLE THE NUMBER THAT BEST DESCRIBES YOUR BREAST SIZE PRIOR TO TREATMENT)
 
1 The same on both sides
 
2 Larger on right
 
3 Larger on left
 
5 THE SIZE OF YOUR BREASTS NOW IS (CIRCLE THE NUMBER THAT BEST DESCRIBES YOUR BREAST SIZE NOW)
 
1 The same on both sides
 
2 Larger on right
 
3 Larger on left

Initials _____		

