## **2.2 Secondary Objectives**

- To determine if brachytherapy will have non-inferior toxicity to external beam radiotherapy (5%) at 3 years. Grade 3 or higher toxicity will be scored.
- To evaluate cosmesis at each follow-up by utilizing a cosmesis score based on established Harvard criteria.
- To assess patient satisfaction with breast brachytherapy by a questionnaire pre-brachytherapy, at completion, and post-brachytherapy.
- To perform a dosimetric comparison with an external beam plan for each patient. The following parameters will be evaluated: skin dose, target coverage, dose homogeneity index, and NTDmeans from dose volume histograms for each individual patient for heart, lung, and contralateral breast.
- To assess the ability to interpret mammography after interstitial brachytherapy.
- To evaluate Disease-free, Mastectomy-free, and Overall Survival.

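### Item 3 of the Patient Cosmesis Form merges satisfaction with treatment re-choice in overlapping answers, so dissatisfaction and preference for external beam can only be bounded

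*Combined protocol and SAP*

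**What the plan says.** Section 2.2 lists the objective: "To assess patient satisfaction with breast brachytherapy by a questionnaire pre-brachytherapy, at completion, and post-brachytherapy". Section 10.1.4 repeats it under quality of life. Section 10.2 plans summary statistics only; it sets no hypothesis, target or margin for satisfaction.

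Appendix III supplies two patient-completed instruments. The Spitzer index covers activity, daily living, health, support and outlook, and does not ask about satisfaction with treatment. The Patient Cosmesis Form does so once, in item 3. Its general instruction is "Circle only one answer per question", and item 3 adds its own rule: "CIRCLE THE NUMBER NEXT TO THE ITEM THAT BEST DESCRIBES YOUR SATISFACTION". The four answers are:

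- Answer 1: "I am totally satisfied with the treatment and results".
- Answer 2, after an underlined *not*: "totally satisfied, but would choose brachytherapy (radioactive implants) again".
- Answer 3, after an underlined *not*: "totally satisfied and would choose the standard 5 or 6 weeks of external beam therapy if I had it to do over again".
- Answer 4: "I am dissatisfied with the brachytherapy (radioactive implants".

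The stem and answer 1 cover both the treatment and its results. Answer 4 covers the brachytherapy alone. By Sections 8.1 and 9.1 the form is completed before treatment, at 6 and 12 months, and then yearly to 5 years.

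**The concern.** The list asks two things at once: the level of satisfaction, and the treatment the patient would choose if she could decide again. Only answers 2 and 3 record both. A patient who is dissatisfied is also not totally satisfied, so answer 4 does not exclude 2 or 3, and nothing on the form says which takes precedence. Answers 1 and 4 do not record a re-choice.

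A table of code frequencies invites the reader to take code 4 as the percentage dissatisfied and code 3 as the percentage who would rather have had external beam. Each is only a lower bound. Because the form is repeated for 5 years, some movement between codes 2 and 4 or between 3 and 4 may come from a patient picking a different one of two true answers while her opinion stays the same.

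**Working it through.** The documents give no figure for satisfaction, so there is none to reproduce. The check has two parts: which answers can be true together, and what the codes then identify.

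**Overlap**

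- Dissatisfied and would choose brachytherapy again: answers 2 and 4 both fit.
- Dissatisfied and would choose external beam: answers 3 and 4 both fit.
- Totally satisfied: only answer 1 fits.

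**Bounds.** Let p1 to p4 be the shares circling answers 1 to 4.

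- Not totally satisfied = p2 + p3 + p4. This is directly estimable, as is totally satisfied = p1.
- Dissatisfied: at least p4, at most p2 + p3 + p4. If answer 2 is taken to exclude dissatisfied patients, the upper limit falls to p3 + p4.
- Prefers external beam: at least p3, at most p3 + p4. This assumes that totally satisfied patients do not prefer external beam. The interval is exactly p4 wide.

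**Illustration.** The total of 300 comes from Section 10.2. The counts are assumptions, chosen to show a range.

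| Assumed counts, answers 1/2/3/4 | Prefers external beam | Dissatisfied | Dissatisfied, if answer 2 excludes it |
|---|---|---|---|
| 255/30/9/6 | 3.0% to 5.0% | 2.0% to 15.0% | 2.0% to 5.0% |
| 240/30/15/15 | 5% to 10% | 5% to 20% | 5% to 10% |
| 210/30/30/30 | 10% to 20% | 10% to 30% | 10% to 20% |
| 240/57/2/1 | 0.7% to 1.0% | 0.3% to 20.0% | 0.3% to 1.0% |

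For the second row: external beam runs from 15/300 = 5% to (15+15)/300 = 10%. Dissatisfied runs from 15/300 = 5% to (30+15+15)/300 = 20%.

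Sampling error comes on top. Taking the lower exact 95% limit at the lower bound and the upper limit at the upper bound, the second row gives 2.8% to 14.0% for external beam and 2.8% to 25.0% for dissatisfaction. More patients would shrink the sampling part but not the bounds themselves.

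**Extreme case.** Assume 30 of 300 patients (10%) are dissatisfied and would prefer external beam, and nobody else circles 3 or 4. Code 4 can then be anything from 0/300 (exact 95% CI 0% to 1.2%) to 30/300 = 10% (6.8% to 14.0%) with identical opinions, and code 3 moves the opposite way. Codes 3 and 4 together stay at 30/300 = 10% (6.8% to 14.0%) throughout. The combined share is immune to the choice between 3 and 4, but not to the choice between 2 and 4.

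**The case against.** The best defence is the item's own instruction to pick the best-fitting answer. Under it several answers may be partly true, and the list can be read as four descending steps with answer 4 at the bottom. That is a reasonable reading, but the form does not state the ordering. Even if every patient used it, those who circle 4 leave no re-choice, so preference for external beam stays uncertain by the full p4.

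A reader might infer that neither share can be estimated at all. The documents do not support that. Both shares are bounded, the external-beam bound is tight when few circle 4, and the totally satisfied share is directly estimable. Nor is every change between visits suspect: moves between answer 1 and the rest, or between 2 and 3 among patients who are not dissatisfied, keep their meaning.

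It is also fair to say that the plan names neither share as an estimand, and that a four-category distribution is a legitimate summary statistic. The difficulty is that such a summary is only as informative as its categories are distinct.

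Finally, the documents never designate item 3 as the instrument for the Section 2.2 objective. Section 10.1.4 gives a schedule that matches the quality-of-life questionnaire row in Section 8.1, and the cosmesis form is not scheduled at completion of brachytherapy. The link is an inference, drawn because no other supplied form asks about satisfaction. Rewording item 3 would not resolve that difference in timing.

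**Conclusion.** The point holds as a measurement weakness of limited reach. Codes 3 and 4, read alone, are lower bounds for preference for external beam and for dissatisfaction. How wide the bounds are depends on response patterns the documents do not give. In the assumed examples the external-beam interval is between 0.3 and 10 percentage points wide, and the dissatisfaction interval between 13 and about 20 points, or between 0.7 and 10 points if answer 2 excludes dissatisfied patients. The 0% to 10% swing is an assumed extreme that needs all 30 patients to hold both views and to circle the same answer; it should not be read as an expected size.

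The bounds rest on two assumptions: patients circle only answers that are true of them, and totally satisfied patients do not prefer external beam. Only a descriptive secondary objective is affected. The primary endpoint, power and sample size do not change.

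**What to change.** Split item 3 in two:

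- **3a:** an ordered satisfaction scale (for example totally satisfied, mostly satisfied, mostly dissatisfied, totally dissatisfied), with every step referring to both the treatment and its results, as the present stem does.
- **3b:** which treatment the patient would choose if deciding again (brachytherapy, external beam, unsure), asked of every patient whatever her answer to 3a.

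Report the two proportions separately at each post-treatment visit where the form is given. Both shares then become directly estimable. For answers already collected on the present item, report the bounds above and the combined share of codes 3 and 4, and do not label code 4 as the percentage dissatisfied.

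The change needs no added visits, staff or patients. Its cost is continuity: codes 2 and 3 carry over to 3b as brachytherapy and external beam, but codes 1 and 4 do not map, so the within-patient series is partly broken for anyone who has already completed the form. If the form is not revised, reporting the bounds and the combined share is still worthwhile and needs no new data.

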## Appendix III: Physician Cosmesis Form

The physician should not share his evaluation with the patient, as it may influence subsequent patient evaluations.  
 Do not compare to previous evaluations. It is the evolution of cosmetic changes we are studying. Attach cover sheet before submission. Dates are recorded mm/dd/yyyy unless otherwise specified.

DE

1 _____ DATE EVALUATION DONE
 
2 PLEASE ASSESS THE COSMETIC RESULTS OF BREAST CONSERVATION THERAPY AT THIS TIME. (Circle the number next to the word that best describes the cosmetic results.)
 
1 EXCELLENT: when compared to the untreated breast or the original appearance of the treated breast, there is minimal or no difference in the size or shape of the treated breast. The way the breast feels (its texture) is the same or slightly different. There may be thickening, scar tissue, or seroma within the breast but not enough to change the appearance.
 
2 GOOD: there is mild asymmetry between the breasts, which means that there is some acceptable difference in the size or shape of the treated breast as compared to the opposite breast or the appearance of the breast before treatment. There may be some mild reddening or darkening of the breast. The thickening or scar tissue within the breast causes a mild change in its shape or size.
 
3 FAIR: moderate deformity of the breast, with an obvious difference in the shape and size of the treated breast. This change involves 1/4 or less of the breast. There can be moderate thickening or scar tissue of the skin and the breast and there may be obvious color changes.
 
4 POOR: marked change in the appearance of the treated breast involving more than 1/4 of the breast tissue. The skin change may be obvious and detract from the appearance. Severe scarring and thickening of the breast which clearly alters its appearance may be present. In retrospect, the breast may have been better treated by a mastectomy.
	
3 CODE A RESPONSE FOR EACH OF THE FOLLOWING ITEMS
 
1 None    2 Yes, seen on close observation    3 Yes, obvious on casual observation
 
 SKIN TELANGIECTASIA   SKIN ATROPHY   POCK MARKS   HYPERPIGMENTATION   ERYTHEMA   FIBROSIS   SKIN DIMPLING OR INDENTATION   OTHER SIGNIFICANT TREATMENT EFFECTS
 
SPECIFY _____


COMMENTS _____
	

Signature _____
	
_____ Date _____

### Appendix III: Spitzer Quality of Life Index (SQLI)

**Instructions:** Score each item **A** through **E**, either 2, 1, or 0 which describes how you felt **during the last week**. Circle only one answer for each item.

**A ACTIVITY DURING THE LAST WEEK I HAVE:**

- 2 been carrying out my normal activities, working or studying full-time, or nearly so, in usual occupation; or managing own household, or participating in unpaid voluntary activities, whether retired or not.
- 1 been working or studying, in usual occupation or managing own household or participating in unpaid volunteer activities but requiring major assistance or a significant reduction in hours worked or a sheltered situation or was on sick leave.
- 0 not been working or studying in any capacity and not managing own household.

**B DAILY LIVING DURING THE LAST WEEK I HAVE:**

- 2 been self-reliant in eating, washing, toileting and dressing; using public transportation or driving
- 1 been requiring assistance (another person or special equipment) for daily activities and transportation but performing light tasks.
- 0 not been managing personal care or light tasks and/or did not leave own home or institution at all.

**C HEALTH DURING THE LAST WEEK I HAVE:**

- 2 been appearing to feel well or reporting feeling "great" most of the time.
- 1 been lacking energy or not feeling entirely "up to par" more than just occasionally.
- 0 been feeling very ill or "lousy", seeming weak and washed out most of the time.

**Appendix III: Spitzer Quality of Life Index (SQLI)**

D SUPPORT	DURING THE LAST WEEK I HAVE:
2	been having good relationships with others and receiving strong support from at least one family member and/or friend.
1	received or perceived the support from my family and friends as being limited which may be related to my condition.
0	received support infrequently or only when absolutely necessary.
E OUTLOOK	DURING THE LAST WEEK I HAVE:
2	usually been appearing calm and positive in outlook, accepting and in control of personal circumstances, including surroundings.
1	sometimes been troubled because not fully in control of personal circumstances or have been having periods of obvious anxiety or depression.
0	been seriously confused or very frightened or consistently anxious and depressed.
IF YOU HAVE COMMENTS, PLEASE WRITE THEM HERE: _____ _____ _____	
Patient's Initials _____ Date _____	

## Appendix IV: Toxicity Scale

## RTOG Acute Toxicity Scoring

TISSUE	Grade 0	Grade 1	Grade 2	Grade 3	Grade 4
SKIN	No change over baseline	Follicular, faint or dull erythema/ epilation/dry desquamation/ decreased sweating	Tender or bright erythema, patchy moist desquamation/ moderate edema	Confluent, moist desquamation other than skin folds, pitting edema	Ulceration, hemorrhage, necrosis

## RTOG Late Toxicity Scoring

ORGAN TISSUE	Grade 0	Grade 1	Grade 2	Grade 3	Grade 4
SKIN	None	Slight atrophy Pigmentation change Some hair loss	Patch atrophy; Moderate telangiectasia; Total hair loss	Marked atrophy; Gross telangiectasia	Ulceration
SUBCUTANEOUS TISSUE	None	Slight induration (fibrosia) and loss of subcutaneous fat	Moderate fibrosis but asymptomatic Slight field contracture <10% linear reduction	Severe induration and loss of subcutaneous tissue Field contracture >10% linear measurement	Necrosis

### Appendix III: Radiotherapy Treatment/Dosimetry Form

LUMPECTOMY/SEROMA CAVITY MEASUREMENTS			
 -  CM (LENGTH)	 -  CM (WIDTH)	 -  CM (HEIGHT)	 -  cm  V100 (VOL ENCOMPASSED BY 100% ISODOSE LINE)
 -  CM (WIDTH)	 -  CM (HEIGHT)	 -  cm  V150 (VOL ENCOMPASSED BY 150% ISODOSE LINE)	
 -  CM (HEIGHT)	 -  cm  DHI = $\frac{V100 - V150}{V100}$		
TARGET VOLUME MEASUREMENTS		 -  % COVERAGE OF LUMPECTOMY CAVITY/SEROMA BY 100% ISODOSE LINE	
 -  CM (LENGTH)	 -  CM (WIDTH)	 -  % COVERAGE OF TARGET VOLUME BY 100% ISODOSE LINE	
 -  CM (WIDTH)	 -  CM (HEIGHT)	 -  RATIO OF V100/TARGET VOL	
 -  CM (HEIGHT)	 -  TOTAL # OF CATHETERS	 -  CATHETER PLACEMENT TECHNIQUE:	
 -  STEP SIZE OF DWELL POSITIONS (2.5 mm or 5.0 mm)	 -  TOTAL # OF DWELL POSITIONS	 -  1 PRONE TEMPLATE	
 -  TOTAL # OF DWELL POSITIONS	 -  ACTIVITY OF IRIDIUM-192 HDR SOURCE	 -  2 SUPINE US	
 -  SEC TOTAL DWELL TIME	 -  CI	 -  3 SUPINE CT	
 -  HRS TIME SEPARATION B/N ANY 2 HDR FRACTIONS	 -  DAYS ELAPSED TIME B/N MOST RECENT SURGERY AND CATHETER PLACEMENT	 -  4 INTRA-OP	
 -  DAYS ELAPSED TIME B/N CATHETER PLACEMENT AND START OF BRACHYTHERAPY	 -  Gy HDR PRESCRIPTION DOSE	 -  5 OTHER _____	
 -  TOTAL # OF FRACTIONS	 -  WERE PHOTOGRAPHS TAKEN OF THE BREAST WITH CATHETERS IN PLACE?		
 -  TOTAL # OF FRACTIONS	 -  ITDmean OF THE HEART	 -  ITDmean OF THE LUNG	
 -  TOTAL # OF FRACTIONS	 -  ITDmean OF THE CONTRALATERAL BREAST	 -  THE CLOSEST DISTANCE B/N THE 100% ISODOSE LINE AND THE SKIN
